Most common adverse reactions (≥5% and greater than placebo) were headache, nausea, decreased appetite, insomnia, and anxiety. The product label carries suggestions to dose medication at least 9 hours before bedtime, advice we will give patients. It also suggests to "measure heart rate and blood pressure prior to initiating and periodically throughout treatment. Control hypertension before and during therapy. Avoid use in patients with unstable cardiovascular disease, serious heart arrhythmias, or other serious heart problems" and "Use caution in treating patients with a history of

psychosis or bipolar disorders. Consider dose reduction or discontinuation of SUNOSI (solriamfetol) if psychiatric symptoms develop". Our protocol is sensitive to identifying these risk categories.

We do not have reason to believe that individuals taking solriamfetol would be risking greater negative outcomes than those observed in sympathomimetic agents already used for ADHD. Commonly observed side effects associated with the use of these FDA-approved stimulants include insomnia, decreased appetite, dry mouth, headache, or increased pulse. Other less common side effects include irritability, stomach pain, onset of tics, or mood changes. Stimulants have also been associated with more rare, but serious, adverse effects such as sudden death, stroke, and heart attack in adults with a history of heart disease. Side effects of atomoxetine are similar to those of stimulants, but notably include fatigue, nausea, increase in heart rate, increase in blood pressure, sexual side effects, agitation or changes in mood. The label for atomoxetine carries warnings about rare reports of liver failure and of suicidal ideation. If solriamfetol produced side effects similar to these other catecholamine agents, our assessment schedule and clinical expertise give high likelihood of both identifying and supporting any clients who experience such negative experiences.

Confidentiality:

All research-related records initiated as a result of a subject's participation in this study that reveal the subject's identity will remain confidential except as may be required by law. Results of urine or drug pregnancy testing will not become part of the subject's medical record.

Data obtained from this study will not identify the subjects individually. Subjects will be assigned code-names and ID numbers. Data obtained from our studies may be published, but no subjects will be identified individually in these publications. Original research-related records may be reviewed by the Partners Human Research Committee, and regulatory authorities, for the purpose of verifying clinical trial procedures and/or data. Information may be held and processed on a computer. Access to these computerized records will be password protected and restricted to study staff. Subjects will only be contacted regarding future studies if they indicate that they are interested in being contacted by initialing in the specific section of the consent form.

Email communication:

Any email communication will be done using Send Secure encryption per Partners polcy, unless a subject has authorized non-secure email communication. Before sending or responding to an unencrypted email message to an individual, the individual must acknowledge understanding of, and agreement to, accept the risks as communicated to them via the following language "The Partners standard is to send email securely. This requires you to initially set up and activate an account with a password. You can then use the password to access secure emails sent to you from Partners HealthCare. If you prefer, we can send you "unencrypted" email that is not secure and could result in the unauthorized use or disclosure of your information. If you want to receive communications by unencrypted email despite these risks, Partners HealthCare will not be held responsible. Your preference to receive unencrypted email will apply to emails sent from this research group/study only." This language will be copied into an email response to an individual, or may be read over the phone to the individual, or an individual could agree by reading this in person and signing this statement, or simply by agreeing verbally.

VIII. POTENTIAL BENEFITS

There may be no direct benefit to subjects participating in this study. Potential benefits to the participants include education about ADHD, a trial of a supplement that could be continued after the

study, and the opportunity to contribute to medical science and thus help others with similar difficulties.

VIII. Visual Timeline of Key Study Elements

	Eval.	Baseline (Visit 0)	Week	Week 2	Week 3	Week 4	Week 5	Week 6/drop
Consent	х							
Eligibility	х							
Vital Signs (BP, pulse)		X*	х	х	х	х	х	x
Clinician Evaluation	x							
AISRS	х	х	х	х	х	х	х	х
ADHD-RS	X*							х
CGI ratings		х	х	х	х	х	х	х
GAF		х	х	х	х	х	х	х
Adverse Events		x	х	х	х	x	x	х
Concomitant Medications		х	х	х	х	х	х	x
BRIEF-A		X*						х
ASR	X*							
ESS		X*						х
PSQI		X*						х
Pill counting				х		х		х
Pregnancy test	х							х

^{*} Can be completed at either evaluation or baseline visit as long as those visits are within 10 days

^{**}If a subject terminates participation early, all assessments at week 6 will be made at study completion.

IX. Monitoring and Quality Assurance

The Principal Investigator will meet regularly with study staff to address procedural issues and the study coordinator will audit each subject's data within 48 hours of each study visit. Furthermore, all data will be audited by the study statistician with the assistance of the database manager on a regular basis to ensure the progress of the study and confirm that all necessary data is being collected and can be transitioned to the statistical package smoothly. Co-investigators are actively involved in the monitoring and quality assurance of these trials. Periodic quality assurance audits will ensure accuracy and completeness of all subject documents, IRB files and correspondence, and the informed consent documentation.

XI. Telehealth Remote study procedures

Subjects will be offered the option to participate via remote telehealth. Individuals may choose a mixture of in-person and telehealth visits, or just one or the other, as suits scheduling convenience or prudent safety practice. For example, during a public health infectious disease crisis such as the COVID-19 pandemic, risks to participants may be reduced by remote televisits. We will not conduct in-person visits unless approved by Partners healthcare and Massachusetts General Hospital.

Recent Virtual Visit Clinical Growth for COVID-19

Virtual visits are real-time visits between patients and providers using the audio and video capabilities of electronic devices. These visits enable patients to continue their routine and follow-up care with Massachusetts General Hospital providers remotely without having to physically visit a hospital or outpatient facility. Since March 2020, virtual visit capabilities at Mass General have significantly expanded to allow more providers to offer this resource to patients in light of COVID-19. On average prior to March 2020, just over 1,000 clinical virtual visits were completed each month (October 2019 – February 2020) via audio and video. In May 2020, more than 85,000 telehealth visits were completed (includes both via video and audio as well as audio only). Between March and August 2020, Mass General Brigham (the parent company of Massachusetts General Hospital) reported over one million telehealth visits occurred within the greater system.

Technology Platform

The videoconferencing technology which will be used by [name] research group in this protocol is currently being used in clinical practice across Massachusetts General Hospital. It has been approved for use by Partners Information Systems and MGH Health Information Services.

This study leverages a videoconferencing platform where clinicians and patients/participants can use personal computers, tablets, and smartphones to communicate easily and securely using real-time video and audio. Visits will be conducted remotely over the Partners-approved video platform, which is HIPAA-compliant. The technology leverages a waiting room functionality so that the provider must admit the patient from the virtual waiting room into the meeting, thus preventing unauthorized entry.

Set Up (Patient)

We will send a letter to patients/study participants with instructions to set up the program on their personal devices. We will also send emails with a videoconference link and any required login information prior to any visit. When the patient/study participant logs into the meeting, clear and concise instructions will appear that instruct the patient to wait in the waiting room until the provider/researcher joins the room and admits them.

Training/ Resources

The MGH Center for TeleHealth will provide training session(s) to educate the lead investigators on utilizing telemedicine for virtual visits and the Research Assistants on training patients and clinicians to use the technology. The Center will also provide tip sheets and instructions for the team on how to use the technology.

The following elements describe methods we will use to ensure clinical and research standards are maintained when telehealth is utilized in the study.

A. Remote Informed Consent Procedures

Prior to the completion of any study procedures, the study clinician will remotely conduct informed consent procedures with the participant. The study clinician will be a licensed physician and either the Principal Investigator or a coinvestigator. Study staff will provide the participant with an IRBapproved consent form via courier mail service or an encrypted email, unless the subject has formally allowed non-encrypted email, as described elsewhere in this document. In the event that email encryption is waived via verbal consent from the participant, the study coordinator will communicate with them via unencrypted email moving forward. This correspondence will include information about why they are receiving the consent form and directions to inform study staff when the consent form has been received. Study staff will then schedule a time for the study clinician to conduct informed consent procedures with the participant via telephone call. The study clinician will call the participant at the scheduled time and conduct informed consent procedures, per the following existing guidelines: review the informed consent form, explain the risks and benefits of study participation, discuss alternatives to participation, and answer any questions the participant may have. If the participant decides to participate in this study, they will sign the consent form. All written signed form(s) will then be sent via courier mail serivce to the study clinician who performed the informed consent procedures for signature. The study clinician will then send the signed form(s) to the study coordinator via courier mail service. The study coordinator will perform a completeness check prior to the start of any study procedures and provide the participant with a copy of the signed form(s) via courier mail service or (un)encrypted email. Copies of all virtually signed form(s) will automatically be sent to the study clinician, the study coordinator, and the participant.

B. Study Visits via Telemedicine

1. Study Visit Timeline

To accommodate scheduling and communication logistics, elements of the initial evaluation (prebaseline) study visit may occur over more than one day, and other study visits may occur at various points within the same day.

2. Telemedicine

This study will be preferentially conducted by remote telemedicine methods, with option for inperson assessments if needed. Audio and visual communication will be required for evaluation and baseline visits for a subject to participate. If a participant plans to participate by telehealth only, participants with predictable lack of access to audio and visual means of communication will not be enrolled in the study.

All telehealth study visits and study procedures (excluding informed consent procedures) will be conducted via the MGH telemedicine platform, TeleHealth, which is maintained by Partners HealthCare. In the event that TeleHealth malfunctions or the participant does not have access to a device compatible with the TeleHealth platform, the study visit will be completed via secure Zoom web interface, or if not possible, by telephone call. If at any point during a telemedicine study visit, the participant endorses any safety concerns or any acute clinical issues emerge, the study clinician will take the necessary steps to ensure the participant receives the appropriate follow-up clinical care.

3. Clinician Assessments and Rating Scales

As demonstrated by the prior incorporation of telemedicine study visits in studies conducted by our research unit, clinician assessments and rating scales can safely and effectively be completed remotely. The study clinician will enter data into REDCap for televisits, a secure, HIPAA compliant web-based application hosted by Partners HealthCare Research Computing, Enterprise Research Infrastructure and Services (ERIS).

4. Informant Assessments and Rating Scales

Informant assessments and rating scales can safely and effectively be completed remotely via REDCap as well. The study coordinator will provide the participant with an online link and access code to these REDCap questionnaires via (un)encrypted email.

5. Safety Measures

Urine Pregnancy Screen

Women of child-bearing potential will complete a urine pregnancy test as part of the evaluation study visit and Week 6/drop study visits. Study staff will order a urine pregnancy test online and ship it directly to the participant's home address. The test will be ordered and shipped in advance to ensure delivery prior to the applicable study visit. On the day of the visit, the participant will complete the test after the study coordinator or a study clinician has reviewed the proper procedure for completing the test. In addition, the participant will provide the study coordinator with visual confirmation of the result via TeleHealth video system or image sent by (un)encrypted email.

Vital Signs

The study coordinator will ship a blood pressure and heart rate monitor to each participant, and ask the participant to self-report the vital signs on the same day as the study visit via telephone call or image sent by (un)encrypted email. The study coordinator will note that these data points were provided by study subject report, rather than study staff measurement.

III. Remote Study Medication Dispensation

Study medication will be stored at, ordered from, and dispensed by the MGH Clinical Trials Pharmacy (CTP). Study staff will pick the study medication that is assigned to each participant from the MGH CTP, remaining blinded to whether it is active or placebo product, and send it via courier mail service directly to the participant's home address. Staff will be trained to follow all guidelines elaborated by the MGH CTP and Drug Enforcement Agency in this process. The study medication will be ordered and shipped in advance to ensure delivery prior to the baseline study visit, with sufficient supply to cover partipation throughout the study. Participants will be given 75 mg strength size active/placebo pills, such that they can take one or two to make up 75 mg or 150 mg per daily dose. Individuals will be given clear instructions to adhere to the agreed-upon dosing schedule between study visits, must keep the study agent in a safe place where other's would not take it in error, must not divert any study agent, and must return study agent to the investigators at the end of the study. Returns will be done either in person at end of study visit or by same-day courier pickup. Where possible, study medication orders for participants from this and other studies within this department will be coordinated so that they can be picked up and mailed in bulk. The study coordinator retrieving study medication orders will be listed as a member of study staff on all applicable studies. Per standard research procedure, the study clinician will record reported medication compliance in the applicable Chart Note. After the completion of study participation, the participant will send the leftover study medication and bottles to the study coordinator via mail courier service. The study coordinator will complete a thorough capsule count at that time and maintain the study medication until it can be returned to MGH and discarded in a biohazard container.

XI. REFERENCES

- 2. Murphy, K., & Barkley, R. A. (1996). Attention deficit hyperactivity disorder adults: comorbidities and adaptive impairments. *Comprehensive Psychiatry*, *37*(6), 393-401.

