Solriamfetol is a dopamine and norepinephrine reuptake inhibitor that the FDA has approved for treatment of excessive daytime sleepiness in patients with narcolepsy or obstructive sleep apnea²². It is a class IV controlled substance, and clinical trials suggest it is well tolerated. Conventional therapies for ADHD, including the stimulants methylphenidate and mixed amphetamine salts, and the nonstimulant atomoxetine, are thought to work in part through reuptake blockade and/or increased release of the catecholamines dopamine and norepinephrine. ¹³ Prior studies with modafinil and bupropion and mazindol also suggest ADHD benefit from these agents with dopamine and norepinephrine reuptake properties. Solriamfetol is thought to support dopamine and/or norepinephrine activity.

Prior clinical data to support efficacy in sleep disorder indications, and the product's well-elaborated safety profile, also suggest potential favorable application for ADHD care. Other agents approved by the FDA for ADHD are closely controlled substances (stimulant agents) or may take longer to work than first-line stimulants or have less effect than stimulants (e.g. atomoxetine and

guanfacine). If Solriamfetol had moderate effect size for ADHD symptoms, it may open up an option for a new method of treating ADHD.

Because Solriamfetol could have positive effects on ADHD symptoms, has not been evaluated in ADHD, and is expected to be and well tolerated, we propose to conduct a double-blind pilot study enrolling 60 adults with ADHD. Such a pilot study can determine whether Solriamfetol is likely to have a moderate effect size for this indication. Using a dose-optimization protocol, we will maximize ability to estimate clinical effects. To assess the safety and efficacy of Solriamfetol, we will use ratings of spontaneously reported adverse events and ADHD symptoms as primary outcome measures. Adults with moderate levels of ADHD will be enrolled. We choose to evaluate response over six weeks, as this has been a typical format sensitive to mild to moderate effects on ADHD, allows for dose titration, and sufficient exposure durations for participants to notice and evaluate a clinically useful effect.

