- 12. Concomitant medications with high potential for dopaminergic or sympathomimetic effects.
- 13. Investigator and his/her immediate family; defined as the investigator's spouse, parent, child, grandparent, or grandchild.
- 14, Reasonable suspicion of inability, in the judgement of the investigator, to appropriately monitor experiences during the study and take steps to report these experiences or respond in a manner preserving personal health and safety.
- 15. If clinically appropriate, any subjects taking medication exclusionary to the study (including agents used for management of ADHD) must be tapered off this medication prior to baseline visit for the length of 5 half-lives of the medication, corresponding to 95% of the agent leaving the participant's system), plus several days or otherwise sufficient period of time to allow assessment of eligibility for participation off medication.
- 16. Any condition, including a moderate to severe untreated sleep disorder or other mental health disorder, that renders inability, in the investigator's judgement, to determine whether ADHD symptoms are primarily due to ADHD.

IV. SUBJECT ENROLLMENT

Informed consent will be obtained prior to the performance of any protocol procedures and prior to administration of study drug. The informed consent document will be used to explain in simple terms the risks and benefits of study participation to the subject. The nature of the study will be fully explained to the subject by a board-certified physician who is either the primary investigator or a co-investigator. The subject will be encouraged to ask questions pertaining to their participation in the study and the subject may take as much time as they feel is necessary to consider his/her participation in the study as well as consult with family members or their physicians. Participation in this study is voluntary and the subjects may withdraw from the study at any time. The IRB-approved informed consent documents will be signed and dated by the subject and the physician obtaining consent.

V. STUDY PROCEDURES

We will conduct a 6-week double-blind pilot clinical trial exploring efficacy and tolerability of solriamfetol in adults with ADHD who fulfill the inclusion and exclusion criteria for participation. Enrollment will stop once 60 subjects have consented and been exposed to study agent or placebo.

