Randomization to active or placebo will occur once a subject is scheduled for a baseline visit, when the clinical trials pharmacy will be given a subject name that the pharmacy will associate with a number identifier. We have extensive experience maintaining blinding, wherein we have our central Mass General Hospital Clinical Trials Pharmacy pharmacy serve as the only part of the greater trial team that is aware of the assignment to active or placebo during study participation. The trials pharmacy will receive products identified by the sponsor as active or placebo fill, over-encapsulate these products to look identical, bottle these products with unique identifiers, maintains the placeboactive ratio, and maintain blinding until study completion. For the purpose of the final analysis, the official clinical database will not be unblinded until medical/scientific review has been completed, protocol violators have been identified (if appropriate), and data collection has been declared complete. In the extreme event where subject safety will be compromised by maintaining the blind, eg. an adverse event where treatment is dependent on knowing if they were on active or placebo medication, we will unblind the status of the subject's study agent, following emergency protocols in place in our department and institution.

Assessments and Instruments:

Our primary endpoint will be change in the Adult ADHD Investigator Symptom Rating Scale (AISRS), the instrument we will use to evaluate ADHD symptom burden. We also will evaluate spontaneously reported adverse events as our main outcome of tolerability. At screening evaluation, AISRS ratings and concurrent medication treatments will be recorded. In addition, at screening or baseline, a brief demographic interview will be conducted to obtain information used to calculate socioeconomic status.

Demographic information, including socioeconomic status data, will collected for each participant.²⁴

During the study, the following assessments and instruments will be used:

Clinician rated assessments (rated at each in-office study visit, unless otherwise noted):

- Global Assessment of Functioning (GAF) scale. The GAF will assess global functioning using a scale from 1 (worst) to 100 (best). This will be collected at all study visits, excluding the screening visit.
- Clinical Global Impressions (CGI) scale for ADHD. The CGI is a measure of illness severity, improvement, and efficacy of treatment.

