Examples of individuals who will discontinue study participation include those who: 1) develop intolerable adverse events (AEs) despite dose adjustments; 2) have (a) clinically relevant serious AE(s) as determined by the investigator; 3) have worsening ADHD symptoms (much worse or very much worse as rated on CGI-Improvement at two consecutive visits); or 4) have emergent adverse mental health state including psychosis, suicidality, substance use, or worsening mood and/or anxiety; 5) are non-adherent to study procedures or withdraw from the study; 6) intend to be or become pregnant.

If study participation is discontinued due to safety reasons, participants will receive two followup visits, giving adequate time for appropriate psychiatric referrals to treaters in their communities. Subjects found to be taking substances listed as exclusionary during the course of the study may be discontinued based on PI evaluation of their eligibility.

VI. BIOSTATISTICAL ANALYSIS

Data processing and management followed procedures developed by the investigators and used in ongoing studies. Up to 30 subjects will receive Solriamfetol, and up to 30 subjects will receive placebo. Changes in outcome ratings within and between study groups will be tested.

Hypothesis 1 will be our main testable hypothesis, tested by evaluating whether the group receiving stimulant treatment has a significantly greater improvement in ADHD symptom rating. We will also explore exploratory hypotheses. This will include comparing the active and placebo arms on: the rate of individuals achieving an a priori definition of clinical improvement, with at least a 25% reduction in ADHD symptoms, and a CGI of much or very much improved (1b), and the rate of reduced symptoms of executive dysfunction (defined by a 0.5 standard deviation improvement on BRIEF-A self-report total or subscale scores) (1c).

All other analyses will be exploratory and p-values will be reported as nominal, and not used to infer significance. We will also explore descriptively whether baseline sleep problems, sleepiness, or deficits in domains of the BRIEF predict improvement on AISRS or BRIEF ratings.

Our primary test of Hypothesis 2 will be review of the occurrence of moderate or severe adverse events, and description of reasons for study dropout. We will also report rates of the same adverse event in active and placebo arms occurring two or more times for a particular subject.

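### The plan says the pilot can determine whether a moderate effect is likely, but at 30 per arm with no stated baseline adjustment that capability is weak and unsupported

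*Combined protocol and SAP*

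**What the plan says.** Section I (Background and Significance) introduces the design in these words: "we propose to conduct a double-blind pilot study enrolling 60 adults with ADHD". It then states what that design can deliver: "Such a pilot study can determine whether Solriamfetol is likely to have a moderate effect size for this indication". No number is attached to the word moderate.

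Section VI (Biostatistical Analysis) gives the size: "Up to 30 subjects will receive Solriamfetol, and up to 30 subjects will receive placebo". Under Study Procedures, recruitment is tied to exposure, not completion: "Enrollment will stop once 60 subjects have consented and been exposed to study agent or placebo".

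The primary endpoint, in Section V under Assessments and Instruments, is change in AISRS. Section VI decides Hypothesis 1, its main testable hypothesis, by whether the active group "has a significantly greater improvement in ADHD symptom rating". It names no model, covariate, significance level, SD, missing-data method or target precision. The timeline table schedules AISRS at evaluation, at baseline and at every weekly visit to week 6.

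**The concern.** Section I makes the size of the effect the question the study is meant to answer. Nothing in the plan connects that question to the number of subjects or to the analysis. If 30 per arm yields an interval that stretches from no effect to a large one when the estimate is moderate, the study can estimate the effect but can seldom settle whether it is moderate.

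The stake is interpretation. Section I notes that the drug has not been evaluated in ADHD. A reader who takes its sentence at face value and then sees a non-significant primary test could conclude that no moderate effect exists. Under ordinary assumptions, that test result is about as likely as not even when a moderate effect is real. In the other direction, an imprecise favourable estimate could be over-read.

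**Working it through.** **Inputs from the documents.** At most 30 per arm (Section VI); the count is of exposed subjects (Section V); the endpoint is change in AISRS (Section V). There is no stated power or precision figure to reproduce.

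**Inputs assumed, because the documents do not give them.** Two-sided 5% level; moderate = 0.5 SD of AISRS change; unadjusted two-sample t-test; no dropout; 1:1 allocation, inferred from the equal maxima (the pharmacy "maintains the placeboactive ratio", but no ratio is stated).

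**Step 1, precision.** In SD units the standard error is √(2/30) = 0.258. With t(0.975, 58 df) = 2.002, the half-width is 2.002 × 0.258 = 0.517. An observed 0.5 SD would have an interval of 0.5 ± 0.517, from about −0.02 to 1.02.

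**Step 2, power.** The noncentrality is 0.5 / 0.258 = 1.936. The noncentral t distribution with 58 df gives power 0.478. Power of 80% needs a true effect of about 0.74 SD, or 64 per arm at 0.5 SD.

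**Step 3, sensitivity to the assumptions.** Let ρ be the correlation between baseline and week-6 AISRS, with equal SDs at both times.
- The SD of change is √(2(1−ρ)) score SDs, so 0.5 score SD equals 0.42, 0.50 or 0.65 change SDs at ρ = 0.3, 0.5 or 0.7.
- The residual SD after baseline adjustment is √(1−ρ²) score SDs: 0.95, 0.87 or 0.71.
- The variance ratio of adjusted to change analysis is (1−ρ²)/(2(1−ρ)) = (1+ρ)/2: 0.65, 0.75 or 0.85.

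| Case | Power for 0.5 SD | 95% half-width |
|---|---|---|
| Base case (Steps 1 and 2) | 48% | 0.52 change SD |
| One-sided 5% | 61% | – |
| 10% loss, 27 per arm | 44% | 0.55 change SD |
| 20% loss, 24 per arm | 40% | 0.58 change SD |
| 0.5 score SD, unadjusted change, ρ = 0.3 / 0.5 / 0.7 | 36% / 48% / 69% | – |
| 0.5 score SD, adjusted, ρ = 0.3 / 0.5 / 0.7 | 51% / 59% / 76% | 0.49 / 0.45 / 0.37 score SD |
| 0.5 change SD, adjusted, ρ = 0.3 / 0.5 / 0.7 | 66% / 59% / 54% | 0.42 / 0.45 / 0.48 change SD |

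The last row multiplies 0.517 by √0.65 = 0.806, √0.75 = 0.866 and √0.85 = 0.922. The two adjusted rows run in opposite directions because the same 0.5 is measured in different units. That is why the standardiser has to be named.

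The range in the table is 36% to 76%. It covers these cases, not every combination. For example, one-sided 5% with adjustment, score-SD scaling and ρ = 0.7 gives 85%. Unadjusted change with 24 per arm, score-SD scaling and ρ = 0.3 gives 30%.

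**Step 4, what the pilot can still tell apart.** By the normal approximation with standard error 0.258, the chance of observing at least 0.5 SD is 3% if the true effect is 0, 12% if it is 0.2, 50% if it is 0.5 and 88% if it is 0.8. If the true effect is 0, the 95% interval excludes 0.5 SD with the same probability as the power in Step 2, about 48%.

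**The case against.** The strongest reply is that this is a pilot, called so in Sections I and V. It states no power or precision, so no figure of its own is contradicted. The sentence in Section I speaks only of what is likely, and the text that follows it aims at estimating clinical effects. The test in Section VI asks whether the drug beats placebo, not whether the effect is moderate. Hypothesis 1 is directional, so a one-sided test could be defended, and weekly AISRS ratings would permit a repeated-measures analysis.

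Most of this stands, and it limits the point. A reader might infer that the claimed capability is absent; Step 4 shows that the data do discriminate between no effect and a moderate one. A reader might infer that the pilot cannot rule a moderate effect in or out; as an absolute that is false, since under no effect the interval excludes 0.5 SD nearly half the time. A reader might also infer that the plan makes significance its rule for calling the effect moderate, or for dropping the drug; no section contains such a rule.

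The reply does not supply the missing link. A pilot needs no 80% power, but a stated capability needs some basis in its size and analysis, and none is given.

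**Conclusion.** The point holds in a limited form: the wording in Section I is stronger than 30 per arm supports, and the plan offers no rationale for it. With a two-sided 5% level, moderate taken as 0.5 SD of change, an unadjusted t-test and no dropout, power is about 48% and the half-width about 0.52 SD. None of those four assumptions is in the documents, so the 48% should always be quoted with them and with the 36–76% range. Thirty per arm is a ceiling and enrolment stops on exposure, so loss to follow-up can only reduce the number with week-6 data.

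This is a shortfall in justification and wording, together with an unused gain in precision. It is not an internal contradiction, and it does not show that the study is uninformative.

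**What to change.** 1. In Section VI, define the main result as the week-6 AISRS difference between arms, adjusted for baseline AISRS. Report it with its 95% confidence interval in AISRS points, and as a standardised effect with the standardiser named (for example the baseline SD).
2. In Section I, replace the claim to determine with a statement that the study will estimate the effect. Quote the expected interval width for the adjusted analysis, on the same scale as the chosen standardiser and with its assumptions: about ±0.42 to ±0.48 SD of change, or about ±0.49 to ±0.37 score SD, for ρ from 0.3 to 0.7 with 30 per arm analysed. The unadjusted 48% and ±0.52 SD should not be used there, because they describe an analysis that item 1 replaces.
3. In the same place, state that a non-significant result alone will not be read as absence of a moderate effect.

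The cost is wording in two sections and one covariate that is already collected, with no extra patients. The downside is that the stated capability becomes less favourable.
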